Up to approximately 35 Investigators and study centers globally, are expected to participate in this study.

Number of Subjects:

Approximately 96 eligible subjects will be randomly assigned to study treatment for an estimated total of 48 subjects per treatment arm. It is assumed up to 10% of the subjects may drop out, leaving 43 evaluable subjects per arm for the primary endpoint analysis at Week 28.

Treatment Groups and Duration:

The study duration per subject will be approximately 18 to 19 months, and the total duration of the study will be approximately 3 years.

The study consists of a screening period of 28 days, a 52-week treatment period (a 28-week double-blind placebo-controlled treatment period followed by a 24-week double-blind, active treatment period), and a 20-week observational follow-up period.

Part 1: Double-blind, placebo-controlled part, where subjects will receive either tildrakizumab 100 mg (Arm A) or placebo (Arm B) SC at Weeks 0, 4, and 16. At Week 16, subjects who experience significant worsening of plaque psoriasis (defined as an increase in s-PGA by at least 2 from the baseline measurement) will be eligible for an early escape. Subjects selected for early escape by the Principal Investigator at Week 16 will have study medication discontinued and will complete the End of Treatment visit assessment, followed by the observational safety follow-up period.

Part 2: At Week 28, subjects initially randomized to placebo will be switched over to receive tildrakizumab 100 mg at Weeks 28, 32, and 44. Subjects initially randomized to tildrakizumab 100 mg will continue to receive the active drug at Weeks 28, 40, and 52. In order to maintain the blind, subjects in both treatment arms will receive matching placebo injections at specified time

points as described in the SoA. Subjects who experience significant worsening of plaque psoriasis at Week 28 (defined as an increase in s-PGA by, at least 2 from the baseline measurement) will be discontinued from treatment.

Part 3: After Week 52 (or early termination of study treatment prior to Week 52), subjects will enter the 20-week observational safety follow-up period when tildrakizumab treatment will be stopped.

Statistical methods:

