To assess the effect of tildrakizumab on nail pain compared with placebo as measured by nail pain NRS score improvement at Week 28.	• The proportion of subjects with at least a 30% decrease in Nail Pain NRS score from Baseline at Week 28 in subjects with a baseline nail pain NRS score of > 3*.

EVELODATODY OD JECTIVES	EVDLODATODY ENDDOINTS
 EXPLORATORY OBJECTIVES To assess the effect of tildrakizumab over time 	• Change from Baseline in mNAPSI, NAPSI,
at measured time points through Week 52 as measured by mNAPSI, NAPSI, Nail Pain NRS, BSA, PGA-S, static Physician's Global	Nail Pain NRS, BSA, PGA-S, sPGA, PASI,
Assessment (s-PGA), PASI, To assess the effect of tildrakizumab on Quality of Life (QoL) as measured by: Dermatology Life Quality Index (DLQI) and Nail Assessment in Psoriasis and Psoriatic Arthritis QoL (NAPPA- QoL).	Change from Baseline in DLQI score (total and 6 domain scores) and NAPPA-QoL score at measured time points through Week 52.
 To assess the effect of tildrakizumab measured by using anchor scales: Clinician Global Impression of Change (CGIC) Clinician Global Impression of Severity (CGIS) Patient Global Impression of Change (PGIC). Patient Global Impression of Severity (PGIS). Patient Global Impression of Severity for pain (PGIS-P). Patient Global Impression of Change for pain (PGIC-P). 	Change from Baseline in CGIC, CGIS, PGIC, PGIC-P, PGIS, and PGIS-P at measured time points through Week 52.
SAFETY OBJECTIVE	SAFETY ENDPOINT
To assess the safety and tolerability of tildrakizumab in subjects with moderate to severe nail psoriasis over 52 weeks.	 The percentage of subjects with incidence, seriousness, and severity of all adverse events. The percentage of subjects with severe infections defined as any infection meeting the regulatory definition of a serious adverse event (SAE), or any infection requiring intravenous (IV) antibiotics, whether or not reported as a serious event as per the regulatory definition. The percentage of subjects with malignancies (excluding carcinoma in situ of the cervix). The percentage of subjects with non-melanoma skin cancer.

The percentage of subjects with melanoma
skin cancer.
The percentage of subjects with MACE.
The percentage of subjects with study
treatment-related hypersensitivity reactions
(e.g., anaphylaxis, urticaria, angioedema,
etc.).
The percentage of subjects with injection
site reactions (e.g. pain, erythema, edema
etc.).

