2 PROTOCOL SUMMARY

2.1 Study Design

This is a multicenter, randomized, double-blind, placebo-controlled study to assess the efficacy and safety of tildrakizumab in the treatment of moderate to severe psoriasis of the nails. Approximately 96 eligible subjects (approximately 48 per arm) with moderate to severe plaque psoriasis and concomitant moderate to severe nail psoriasis will be randomized into the study. Eligible subjects will be randomized to one of the 2 arms in a 1:1 ratio: Arm A: Tildrakizumab 100 mg, SC (n = 48) and Arm B: Placebo, SC (n = 48). The study is planned with a primary analysis, which will be performed when the last subject has completed the Week 28 visit and a final analysis to be performed when the last subject has completed the study.

The study will comprise 3 parts:

PART 1: Double-blind Placebo-controlled (Day 1 to Week 28)

After a Screening Period of up to 28 days and on Day 1, all eligible subjects will be randomized 1:1 to receive either tildrakizumab 100 mg or placebo administered by SC injection on Week 0 (Day 1), Week 4, and Week 16. Subjects should receive the first dose of study treatment within 24 hours of randomization. The treatment period for the double-blind placebo-controlled part of the study is 28 weeks.

Early Escape: At Week 16, subjects who experience significant worsening of plaque psoriasis (defined as an increase in Static Physician's Global Assessment [s-PGA] by, at least, 2 from the baseline measurement) will be eligible for early escape. Subjects selected for early escape by the Principal Investigator at Week 16 will have study medication discontinued, and will

| Effective Date: 10-AUG-2020 | Page 9 of 61 |
|-----------------------------|--------------|

complete the End of Treatment visit assessment, followed by the observational safety follow-up period. Subjects entering early escape will not be replaced for purpose of statistical analysis and will be included in the appropriate analysis populations as defined in Section 3.5.

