Following the last subject's Week 28 visit (or early termination prior to Week 28), Week 28 analysis may be conducted on available data to evaluate safety and efficacy, and a Week-28 clinical study report (CSR) may be developed after database lock (DBL). In this case, when all the randomized patients have either completed the Week 28 evaluations or have stopped study participation prior to the Week 28 visit, the first database freeze (DBF) will occur (referred to as Week 28 DBF hereafter). When all patients randomized in this trial have either completed the Week 72 evaluations or have ceased study participation prior to the Week 72 visit, the second DBL will take place [referred to as the Final (Week 72) DBL henceforth], and subsequent CSR will be generated. The sponsor might opt to have a single DBL and CSR at the last subject's Week 72 visit (or early termination prior to Week 72) without a DBL at Week 28.

All assessments in PART 1 are scheduled to happen before or on the date of injection at Week 28. The analysis of efficacy and safety endpoints for PART 1 will follow the analysis visit window and definitions as specified in the sections below.

PART 2: Double-blind Active Treatment Extension (Week 28 to Week 52)

At Week 28, subjects initially randomized to placebo will be switched over to receive tildrakizumab 100 mg at Weeks 28, 32, and 44. Subjects initially randomized to tildrakizumab 100 mg will continue to receive tildrakizumab at Weeks 28, 40, and 52. In order to maintain the blind, subjects in both treatment arms will receive matching placebo injections at specified time points as described in the Schedule of Activities (SoA) in the Clinical Protocol.

Subjects who experience significant worsening of plaque psoriasis at Week 28 (defined as an increase in s-PGA by, at least, 2 from the baseline measurement) will be discontinued from treatment. Subjects who do not fulfill this criterion at Week 28 will continue to receive tildrakizumab in Part 2 as described above.

All assessments in PART 2 are scheduled to happen after the date of injection at Week 28 and before or on the date of injection at Week 52. The analysis of efficacy and safety endpoints for PART 2 will follow the analysis visit window and definitions as specified in the sections below.

PART 3: Observational Safety Follow-up (Week 52 to Week 72)

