10 SAFETY ENDPOINTS

The safety and tolerability of the study drugs are determined by reported adverse events (AEs), physical examinations, electrocardiogram results (ECGs), vital signs, and laboratory test results (Hematology, Biochemistry, and Urinalysis), and Columbia-Suicide Severity Rating Scale (C-SSRS).

| Effective Date: 10-AUG-2020 | Page 40 of 61 |
|-----------------------------|---------------|

All safety summaries will be based on the entire SAF.

Following reporting of Week 28 results, a group comprising formerly placebo-treated subjects who migrate to tildrakizumab 100 mg for the remainder of the study will be identified for reporting at the end of the study.

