| Effective Date: 10-AUG-2020 | Page 41 of 61 |
|-----------------------------|---------------|

Non-TEAEs will be listed only and will not be included for analysis and summarization.

All AEs will be presented in a by-treatment and by-subject listing for Part 1, detailing the verbatim term, SOC, PT, injection site reaction or not, related to study indication or not, start date, stop date, time since most recent dose of IP, severity, outcome, relationship to study drug, action taken regarding study drug, other action taken, seriousness and criteria for seriousness. Serious AEs (SAEs) and TEAEs leading to study medication discontinuation, AEs of Special Interest (AESI), and events of clinical interest (ECI) will also be presented in separate listings.

An AE profile for the SAF will be provided for Part 1, Parts 2 and 3, and overall, which summarizes the subject incidence, by treatment received for the following information:

- Any TEAEs;
- Drug-related TEAEs;
- Any TEAEs with an outcome of death;
- Treatment-emergent SAEs;
- Drug-related treatment-emergent SAEs;
- TEAEs leading to discontinuation of study medication;
- Drug-related TEAEs leading to discontinuation of study medication;
- Any AEs of special interest, including:
 - Injection site reactions
 - Severe infections
 - o Malignancies (excluding carcinoma in situ of the cervix).
 - Non-melanoma skin cancer
 - Melanoma skin cancer
 - Major Adverse Cardiovascular Events (MACE)
 - Study treatment-related hypersensitivity reactions (e.g., anaphylaxis, urticaria, angioedema, etc.).

| Effective Date: 10-AUG-2020 | Page 42 of 61 |
|-----------------------------|---------------|

Study treatment-related hypersensitivity reactions will be identified based on Sponsor review of treatment-blinded listings of AE preferred terms prior to declaration of the IA DB freeze.

The number and percentage of subjects with TEAEs will be summarized for each treatment arm and/or in total by SOC and PT. Drug-related TEAEs, TEAEs leading to discontinuation of study drug, drug-related TEAEs leading to discontinuation of study drug, treatment-emergent SAEs, and drug-related treatment-emergent SAEs, AESI and ECI will be summarized in the same manner. For these summaries, subjects with multiple AEs will be counted only once per SOC and PT.

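### The overall adverse event tables plan crude percentages by treatment received, which may set 28 weeks of placebo time beside 44 to 72 weeks after starting tildrakizumab

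*SAP*

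**What the plan says.** The Protocol synopsis sets out "a 28-week double-blind placebo-controlled treatment period followed by a 24-week double-blind, active treatment period", "and a 20-week observational follow-up period". SAP 2.1 gives the crossover: "At Week 28, subjects initially randomized to placebo will be switched over to receive tildrakizumab 100 mg". No placebo group is planned after that visit.

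For adverse events, SAP 10.1 says "An AE profile for the SAF will be provided for Part 1, Parts 2 and 3, and overall", and describes the profile as one "which summarizes the subject incidence, by treatment received for the following information". The severity, relationship and common-event tables use the same three periods and the same grouping. The system organ class and preferred term tables give numbers and percentages of subjects, by arm and/or in total. Events are assigned to Part 1 or to Parts 2 and 3 according to whether they start after the Week 28 injection.

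Two statements bear on columns and denominators. SAP Section 10 bases all safety summaries on the whole safety set. It also says that, for end-of-study reporting, "a group comprising formerly placebo-treated subjects who migrate to tildrakizumab 100 mg for the remainder of the study will be identified". The columns of the overall tables are not defined further.

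Protocol 9.4.2 groups safety by treatment arm. Protocol 9.4.2.1 mentions incidence rates but gives no time denominator. The safety objective in Protocol 3.0 reads: "To assess the safety and tolerability of tildrakizumab in subjects with moderate to severe nail psoriasis over 52 weeks".

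**The concern.** A crude percentage rises with the time a subject is watched. If events are credited to the treatment being received, a placebo subject who continues in the study contributes at most 28 weeks before switching. Tildrakizumab is credited with 44 or 72 weeks per subject. Placed side by side as percentages, the two would differ even if the drug had no effect on event risk.

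The overall tables are among those that serve the longer safety objective. They cover the events of special interest: severe infections, malignancies, major cardiovascular events, hypersensitivity and injection site reactions. A reader of the clinical study report who compares columns there could take a difference in observation time for a drug effect.

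**Working it through.** **Planned follow-up reproduced.** 28 + 24 + 20 = 72 weeks in all, and 72 − 28 = 44 weeks after the switch. This matches the final visit at Week 72.

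**Time by treatment received.** Assume 48 subjects per arm (SAP 2.1) and no dropout.
- Placebo: 48 × 28 = 1,344 person-weeks.
- After starting tildrakizumab: 48 × 72 + 48 × 44 = 3,456 + 2,112 = 5,568 person-weeks.
- Ratio: 5,568 / 1,344 = 4.1.

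**Effect on crude percentages.** The documents give no adverse event rate, so I assume the same constant hazard on both treatments and vary the 28-week incidence p. Incidence over w weeks is

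I(w) = 1 − (1 − p)^(w/28).

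For p = 10%: I(44) = 1 − 0.90^(44/28) = 15.3%, and I(72) = 1 − 0.90^(72/28) = 23.7%. A pooled any-tildrakizumab column with equal arms is the mean of the two. The rate per 100 person-years is −ln(1 − p) / (28/52.18) × 100.

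| Placebo, 28 wk | Switchers, 44 wk | Original active, 72 wk | Pooled tildrakizumab | Pooled minus placebo (points) | Rate per 100 person-years, every column |
|---|---|---|---|---|---|
| 5% | 7.7% | 12.4% | 10.1% | 5.1 | 9.6 |
| 10% | 15.3% | 23.7% | 19.5% | 9.5 | 19.6 |
| 20% | 29.6% | 43.7% | 36.6% | 16.6 | 41.6 |
| 30% | 42.9% | 60.0% | 51.5% | 21.5 | 66.5 |
| 50% | 66.4% | 83.2% | 74.8% | 24.8 | 129.2 |

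The percentages drift apart while the rate is the same in every column.

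**If the overall columns follow treatment sequence.** Planned follow-up is 72 weeks against 72 weeks, so a 10% event at 28 weeks shows 23.7% in both and no excess is built in. In the placebo-to-tildrakizumab column, however, 28/72 = 39% of planned time is placebo time, so the column gives neither a placebo nor a tildrakizumab incidence.

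**Parts 2 and 3.** Both former arms have 44 planned weeks, all after a tildrakizumab injection at Week 28: 15.3% against 15.3% for the 10% event. The weakness here is the denominator. If the whole safety set is used, subjects who left before Week 28 are counted although they cannot have an event in a window that opens with that injection. For the 30% event, 42.9% becomes 42.9 × 0.90 = 38.6% if 90% reach Week 28, and 42.9 × 0.80 = 34.3% if 80% do (retention assumed). The arm with more Part 1 losses is diluted more.

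SAP 3.3 also dates Part 3 for early terminators from their last injection plus 28 days, whereas SAP 10.1 dates Parts 2 and 3 from the Week 28 injection. The two sections need to be reconciled for subjects who never received that injection.

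**The case against.** The strongest reply is that grouping by treatment received may be no more than the rule that allocates a safety-set subject to the arm actually received, not a split of each subject's time. Protocol 9.4.2 summarises by arm, SAP 10.1 gives organ class and preferred term tables by arm and/or in total, and SAP Section 10 identifies the switchers as a group. All of this is compatible with columns by sequence, where planned follow-up is equal. That stands: the excess is conditional on a layout that the SAP does not fix. It does not remove the need to fix it, because identifying the switchers as a group fits a three-column layout just as well.

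It is also true that Part 1 has its own profile over equal time, that the 52-week safety objective does not ask for a placebo comparison, and that safety is descriptive, so no test is invalidated. These points limit the importance of the matter.

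A reader might infer that the Parts 2 and 3 tables carry the same 28-against-72-week imbalance. They do not: no placebo treatment remains in that window, and both former arms are planned for 44 weeks. A reader might also describe the original active arm as having 72 weeks on drug. The last 20 of those weeks are observation with no further study treatment.

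**Conclusion.** The point holds for the overall tables, conditionally. The measure described is a crude percentage, the columns are undefined, and the literal grouping sets unequal observation times side by side. On that reading, and with an equal constant hazard and no dropout, the pooled tildrakizumab column would exceed placebo by about 5 points for a 5% event and about 25 points for a 50% event, with no drug effect. Events clustered soon after dosing, as injection site reactions may be, would give a smaller artefact.

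The documents do not support saying that the tables will show a false excess: under sequence columns there is none. For Parts 2 and 3 the only point is the denominator.

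One limit remains. The text of SAP Section 8 (exposure) and Section 16 (list of tables) was not available, so exposure-adjusted tables planned there cannot be excluded. This is a cheap improvement to descriptive tables. It is not a threat to the primary result.

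**What to change.** In SAP 10.1:

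1. **Overall tables.** State the columns. For adverse events and events of special interest, add exposure-adjusted incidence rates by treatment at onset: subjects with a first event per 100 subject-years at risk, with 95% confidence intervals.
2. **Time at risk.** Define it to include the safety follow-up. For switchers, start the tildrakizumab clock at the Week 28 injection, and say whether an event during placebo removes a subject from the later risk set.
3. **Part 1.** Keep crude percentages; planned time is equal there.
4. **Parts 2 and 3.** Use as denominator the subjects who received the Week 28 injection, not the whole safety set. Say where events in early terminators are reported.

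No new data are needed. The cost is some programming and extra table columns. If Sections 8 or 16 already provide these rates, a cross-reference from SAP 10.1 meets the request for rates; items 2 and 4 still need to be stated if they are not covered there.

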6.1 Study Treatment Administered

Study treatment details are provided in Table 3.

Table 3: Study Treatment Details

Study Treatment Name:	Tildrakizumab	Placebo	
Dosage Formulation:	Tildrakizumab will be available as a prefilled syringe (PFS) with 100 mg of tildrakizumab and 1 mL solution. Each PFS will contain tildrakizumab solution and the following inactive ingredients: L-Histidine, L-Histidine Hydrochloride Monohydrate, Sucrose, and Polysorbate 80	The placebo formulation is similar to the tildrakizumab without the active ingredient. It will be available in PFS containing 1 mL solution and the following inactive ingredients: L-Histidine, L-Histidine Hydrochloride Monohydrate, Sucrose, and Polysorbate 80.	
Unit Dose Strength/Dosage Level:	100 mg	-	
Route of Administration	SC	SC	
Dosing Instructions:	All the subjects will be dosed at the same time points to maintain the study blinding throughout the study.		
For SC injections, tildrakizumab/placebo is supplied in a with a safety device. Each PFS is assembled with a safet accidental needle sticks. Subcutaneous injections should be rotated with each dos into moles, scars, tattoos, or areas where the skin is tend not intact. Abdominal administration is the preferred site for SC do		with a safety device to prevent with each dose and should not be given ne skin is tender, bruised, red, hard, or	
Packaging and Labeling	Tildrakizumab will be provided in PFS. Each PFS will be labeled as per country requirements.	Placebo will be available in identical containers with the same excipients (with no active drug)	

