6.4 Study Treatment Compliance

The prescribed dosage, timing, and mode of administration may not be changed. Any departures from the intended regimen must be recorded in the eCRFs.

On Week 0 (Day 1), Weeks 4, 16, 28, 32, 40, 44, and 52 the study treatment will be administered at the study center by appropriately trained staff.

Study treatment accountability and subject compliance will be documented throughout the treatment periods (Part 1 and Part 2) using study-specific study treatment dispensing record forms. If a subject does not receive the scheduled dose, every effort should be made to administer the dose as soon as possible.

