3.6 Treatment Assignment

The study treatment in this study is tildrakizumab and placebo. All subjects will be dosed at the same time points to maintain the blind throughout the study. The study arms will receive study treatment during the course of the study as follows:

Arm A:

| Effective Date: 10-AUG-2020 | Page 20 of 61 |
|-----------------------------|---------------|

- Tildrakizumab 100 mg SC injections at Weeks 0, 4, 16, 28, 40 and 52.
- Placebo injections at Weeks 32, and 44.

Arm B:

- Placebo injections at Weeks 0, 4, 16, 40, and 52.
- Tildrakizumab 100 mg SC injections at Weeks 28, 32 and 44.

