TEAEs by maximum severity and TEAEs by relationship to study treatment, and commonly occurring TEAEs, i.e., those that occur in 1% or more of the subjects in either treatment arm, will be summarized by SOC and PT by treatment received in Part 1, Parts 2 and 3, and overall.

Injection site reactions will be described in a by-subject listing and may be summarized separately if deemed necessary.

COVID-19 related adverse events may also be summarized separately if deemed necessary.

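### After Week 28, reactions to the two blinding placebo injections are counted under tildrakizumab in the injection site reaction percentages

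*SAP*

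**What the plan says.** SAP section 3.6 sets out the injections. Arm A: "Tildrakizumab 100 mg SC injections at Weeks 0, 4, 16, 28, 40 and 52" and "Placebo injections at Weeks 32, and 44". Arm B: "Placebo injections at Weeks 0, 4, 16, 40, and 52" and "Tildrakizumab 100 mg SC injections at Weeks 28, 32 and 44". Protocol section 6.0 gives the same schedule, and Protocol section 6.4 confirms common dosing visits: "On Week 0 (Day 1), Weeks 4, 16, 28, 32, 40, 44, and 52 the study treatment will be administered". On the placebo syringe, Protocol Table 3 states: "The placebo formulation is similar to the tildrakizumab without the active ingredient". The listed excipients and the 1 mL volume are the same for both products.

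ISRs are a named safety endpoint, expressed as a share of subjects (Protocol Table 2, SAP section 2.3.4), and an adverse event of special interest (Protocol section 8.3.6). SAP section 10.1 places every adverse event that starts or worsens after the Week 28 injection in Parts 2 and 3. It then plans a profile "for Part 1, Parts 2 and 3, and overall, which summarizes the subject incidence, by treatment received", with ISRs among its rows. SAP section 10 defines the former placebo subjects who cross over as a group of their own for end-of-study reporting. Beyond the profile, SAP section 10.1 says: "Injection site reactions will be described in a by-subject listing and may be summarized separately if deemed necessary".

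**The concern.** An ISR is local and belongs to one injection. After Week 28 every subject sits in a group labelled by tildrakizumab, yet two of that subject's five injections are placebo. A subject whose only reaction followed placebo still adds to the tildrakizumab percentage.

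Causality grading does not separate the two, because Protocol section 6.0 defines study treatment as both tildrakizumab and placebo. An injection-level reading of treatment received is possible. It fits poorly with a subject-level count and with the subject-level crossover group.

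Two uses of the result are at stake: quoting the Parts 2 and 3 or overall ISR percentage as the rate for tildrakizumab, and comparing it with the Part 1 percentage. The plan also has no specified use for the injections at which one arm gets active and the other gets placebo, under blind and at the same visit.

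**Working it through.** **Counting injections** (SAP section 3.6).

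- Before Week 28: Arm A has 3 active (Weeks 0, 4, 16); Arm B has 3 placebo (same weeks). There is no mixing.
- From Week 28: Arm A has active at 28, 40, 52 and placebo at 32, 44. Arm B has active at 28, 32, 44 and placebo at 40, 52. Each arm has 3 active + 2 placebo, so 2/5 = 40% are placebo.
- Whole study: Arm A 6 active + 2 placebo; Arm B 3 active + 5 placebo. Both total 8, matching the eight visits in Protocol section 6.4.

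**Effect on subject incidence in Parts 2 and 3.** Let q be the ISR risk per active injection and p the risk per placebo injection. The documents give neither, so q of 1% to 5% with p no higher than q is an assumption. With full attendance and independent injections:

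- any ISR: 1 − (1 − q)³(1 − p)²
- ISR after an active injection: 1 − (1 − q)³

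| q / p (assumed) | Any ISR | After active only | Difference (points) | Ratio | Extra subjects per 48 |
|---|---|---|---|---|---|
| 1% / 1% | 4.90% | 2.97% | 1.93 | 1.65 | 0.93 |
| 2% / 1% | 7.75% | 5.88% | 1.87 | 1.32 | 0.90 |
| 2% / 2% | 9.61% | 5.88% | 3.73 | 1.63 | 1.79 |
| 5% / 1% | 15.97% | 14.26% | 1.71 | 1.12 | 0.82 |
| 5% / 5% | 22.62% | 14.26% | 8.36 | 1.59 | 4.01 |

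**Relaxing independence.** If some people are prone to ISRs, repeat reactions fall in the same subjects and count once. As an illustration, take a beta-binomial with mean 2% for every injection and an assumed intraclass correlation of 0.3. Then a + b = 1/0.3 − 1 = 2.333, a = 0.02 × 2.333 = 0.0467 and b = 2.2867. The chance of no ISR in n injections is the product of (b + i)/(a + b + i) for i = 0 to n − 1. That gives 0.9559 for n = 3 and 0.9405 for n = 5, so incidence is 4.4% against 5.9%, a ratio of about 1.35 instead of 1.63.

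**Comparability with Part 1.** At a constant 2% per injection, active or placebo, three Part 1 injections give 5.88% and five Part 2 injections give 9.61%. The percentage rises although nothing about the product has changed.

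**Overall summary.** At q = p = 2%, Arm A shows 1 − 0.98⁸ = 14.9% for any ISR against 1 − 0.98⁶ = 11.4% after active. If all of Arm B's reactions are counted together, the figures are 14.9% against 5.9%. The text does not say where Arm B's Part 1 placebo reactions go in this summary.

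**Contrast available in Part 2.** With 96 subjects attending fully there are 96 × 3 = 288 active and 96 × 2 = 192 placebo injections. Week 28 is active in both arms. At Weeks 32, 40, 44 and 52 one arm gets active and the other placebo, giving 4 × 48 = 192 of each, with every subject receiving two of each.

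**The case against.** The case for leaving the plan alone has real force.

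- **The controlled comparison is clean.** Part 1 has three injections of one product per randomised arm and is tabulated separately. A reader might infer that the tildrakizumab-versus-placebo ISR comparison is biased; it is not. Nor is Arm A against Arm B within Part 2 distorted by injection numbers, since the mix is 3:2 in both.
- **The planned percentage is not an error.** The endpoint is a share of subjects, and as incidence under the regimen given it is correct. It misleads only when read as attribution to the product.
- **The 1.6-fold figure is near the top of the range.** It needs equal risk and independent injections. Unequal risk brings it to 1.32 or 1.12, and correlation to about 1.35. Both together would move it nearer to 1, and with no placebo reactions there is no inflation.
- **The Part 2 contrast has limits.** After the Week 52 injection the next scheduled visit is Week 72. The earlier Part 2 injections are followed by a visit within 4 to 8 weeks. Week 28 has no concurrent placebo. These injections help, but do not settle the question alone.
- **Some fields are not yet in place.** The ISR flag and the interval since the last dose are specified only for the Part 1 listing, where the problem does not arise.
- **The plan leaves room.** The ISR listing and optional summary could carry this analysis. SAP sections 8, 12 and 16 are not in the available text, so a rule there cannot be excluded.

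All of this stands as a limit on the point. None of it supplies a rule linking a reaction to the syringe content, and the optional summary is not specified to do so.

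**Conclusion.** The point holds as a cheap improvement to descriptive safety reporting. In the Parts 2 and 3 and overall summaries, ISRs after placebo injections are counted under tildrakizumab groups, and the available text does not prevent it. The direction does not depend on assumed rates: any subject reacting only to placebo raises the percentage. The size does. Across the cases worked, the inflation is roughly 1.1- to 1.6-fold, or 1.7 to 8.4 percentage points, which is about 0.8 to 4.0 subjects per 48. These figures rest on assumed per-injection risks of 1% to 5%, placebo risk no higher than active, and full attendance. The point ranges also assume independent injections.

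A reader might go further and conclude that the ISR table should be replaced. The documents do not support that, because the stated endpoint is the share of subjects with any ISR. Efficacy, the Part 1 safety comparison and the between-arm comparison in Part 2 are untouched.

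**What to change.** In SAP section 10.1:

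1. Link each ISR to the content (tildrakizumab or placebo) of the injection before it, using event onset dates, administration records and the unblinded assignment.
2. Extend the ISR flag and the interval since the last dose from the Part 1 listing to Parts 2 and 3.
3. Add one table of ISRs per injection given, active and placebo separately, by Part. Show Weeks 32, 40, 44 and 52 as the concurrent blinded contrast, with and without Week 52 given the long gap to the next visit. Without Week 52, 3 × 48 = 144 injections of each kind remain at full attendance.
4. Keep the planned subject-incidence table for all ISRs. Footnote that each arm also received two placebo injections in Part 2, and add a row for ISRs following an active injection.
5. State where Arm B's Part 1 placebo reactions are counted in the overall summary.

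Arm-level attribution can stay for systemic events. The cost is one table, a paragraph of SAP text and some date-based attribution, which will be least certain after Week 52. No new data and no change to dosing or visits are needed.
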